7.4.16 Bone Marrow Biopsy and Aspirate

An unilateral bone marrow biopsy and aspirate will be done at screening or up to 90 days before study entry. Thereafter, bone marrow biopsy and aspirate will only be required to confirm CR if it was positive at screening. Minimal residual disease assessment should be done on marrow using PCR for t(14;18) detection during screening and repeated when bone marrow assessments are performed as outlined above.

7.4.17 ECG

An electrocardiogram will be conducted during screening to evaluate for clinically significant cardiac arrhythmias.

7.4.18 Biomarkers

40 ml of blood sample [one red top tube (10 ml) and 3 heparin containing green top tubes (30 ml)] will be collected prior to rituximab on Cycle1, Day 1, Cycle 1, Day 15, Cycle 2, Day 1, and on Cycle 7, Day 1. At the time of documented PD, blood biomarker collection should be performed (+/- 4 weeks). These

Proprietary Information of MD Anderson

samples will be transported within 6 hours of collection to [name] laboratory for processing at the [name], at M. D. Anderson Cancer Center (MDACC). Blood from red top and green top tubes will be processed for isolation of serum and PBMC, respectively using standard laboratory protocols. The isolation of serum and PBMC may also be performed at the Clinical and Translational Research Center (CTRC) Laboratory at MDACC using standard laboratory protocols.

7.4.19 Tumor Tissue Biopsy

For subjects with PD on radiologic assessment, a tumor biopsy to confirm PD is optional. Tumor samples may be analyzed by gene expression profiling, immunohistochemistry, flow cytometry, or other methods to define biomarkers that predict response or resistance to lenalidomide, rituximab and ibrutinib therapy.

In consenting patients, core needle biopsies and fine needle aspirates (FNA) will be obtained at Screening by Interventional Radiology from accessible lymph node under ultrasound or CT-scan guidance. At the time of confirmed PD, if a tumor biopsy is planned as part of routine clinical practice, for consenting patients, a fresh tumor sample should be collected for biomarker analyses and processed. Whenever feasible, up to 3 cores will be obtained using 18 or 20 gauge needles as deemed appropriate by an Interventional Radiologist. The three cores will be processed as follows: 1) the first core biopsy specimen will be preserved in RNAlater for microarray studies; 2) second core will be formalin-fixed and paraffin-embedded for IHC; and 3) third core will be snap frozen for DNA, RNA, or protein isolation. FNA sample will be analyzed by flow cytometry. These samples will be transported in RNAlater (core # 1)/formalin (core # 2)/normal saline (cores # 3 and FNA) within 6 hours of collection on ice to [name] laboratory for processing at the [name], at MDACC. If fresh biopsies are not feasible, archival tissue from prior tumor biopsy may be used for biomarker studies.

7.4.20 Determination of FLIPI Score

During the screening phase, subject's FLIPI score will be calculated and recorded as outlined in Appendix 13.7

7.7.21 Determination of Tumor Burden Status

During the screening phase, subject's tumor burden, either high or low will be determined using the GELF criteria as outlined in Appendix 13.8.

8. SUBJECT COMPLETION AND WITHDRAWAL

8.1 Completion

A subject will be considered to have completed the study if he or she has died before the end of the study, has not been lost to follow up, or has not withdrawn consent before the end of the study.

8.2 Treatment Discontinuation

Proprietary Information of MD Anderson

Study treatment will be discontinued in any of the following events:

- Confirmed PD
- Unacceptable toxicity: an intercurrent illness or AE that prevents further study drug administration beyond 28 days
- Treatment discontinuation by subject beyond 28 days
- Investigator decision
- Subject becomes pregnant

All subjects, regardless of reason for discontinuation of study treatment will undergo a treatment termination visit and followed for progression and survival.

8.3 Study Exit/Withdrawal

Exit from study (including all follow up) will occur under the following circumstances:

- Withdrawal of consent for follow-up observation by the subject
- Lost to follow up
- Study termination by the Investigator
- Death

If a subject is lost to follow up, every reasonable effort should be made by the study personnel to contact the subject. The measures taken should be documented.

When a subject withdraws before the completing the study, the following information should be documented:

- Reason for withdrawal
- Whether the subject withdraws full consent (withdraws consent for treatment and all follow up including further contact) or partial consent (withdraws consent to treatment but agrees to participate in follow up visits).

9. STATISTICAL METHODS

9.1 General Considerations:

This is an open-label, Phase 2 study investigating the efficacy and safety of ibrutinib combined with rituximab and lenalidomide in previously untreated subjects with FL. The study will include 60 subjects in one treatment arm.

9.1.1 Response Assessment

Response assessments will be done and recorded by the Principal Investigator. The response criteria are based on the revised criteria for malignant lymphoma described in the Lugano Criteria, international Working Group for NHL (Cheson 2014).

9.1.2 Safety Monitoring

Proprietary Information of MD Anderson

The Principal Investigator or a physician designee will assess each subject to evaluate for potential new or worsening AEs as specified in the Trial Flow Chart, Appendix 13.1 and more frequently if clinically indicated. Adverse experiences will be graded and recorded throughout the study and during the follow-up period according to NCI CTCAE Version 4.03. Toxicities will be characterized in terms regarding seriousness, causality, toxicity grading, and action taken with regard to trial treatment. The study investigators and data coordinators are responsible for entering the data and safety for this study including causality. For both AEs and SAEs, the Investigator will provide a record of the start and stop dates of the event.

Safety data will be monitored by the Principal Investigator and in accordance with institutional policies. The Investigator will record the action taken with the study drugs as a result of an AE or SAE, as applicable (e.g., discontinuation, interruption, or reduction of study drugs, as appropriate) and report if concomitant and/or additional treatments were given for the event. AEs and SAEs will be reviewed on an ongoing basis to identify safety concerns.

For subjects with a history of Hepatitis B or C, standard of care monitoring for viral reactivation will be conducted. Subjects with a history of Hepatitis B will be required to undergo hepatitis B reactivation prophylaxis unless contraindicated.

All SAEs that have not resolved upon discontinuation of the subject's participation in the study must be followed until recovered, recovered with sequelae, not recovered or death (due to the SAE).

Janssen and Celgene shall notify the Investigator via an IND Safety Report of the following information: Any AE associated with the use of study drug in this study or in other studies that is both serious and unexpected, any changes on the investigational brochure or any other safety information that changes the risk/benefit profile of ibrutinib or lenalidomide during the conduct of the study; any finding from tests in laboratory animals that suggests a significant risk for human subjects; including reports of mutagenicity, teratogenicity, or carcinogenicity. The Principal Investigator shall notify his/her IRB promptly of these new serious and unexpected AEs or significant risks to subjects. The Investigator must keep copies of all AE information, including correspondence with Janssen, Celgene, and the IRB, on file.

9.2 Definition of Analysis Populations

The following definitions will be used for the efficacy and safety analysis:

- All treated population: The subjects who enrolled in the study and had at least 1 dose of study drug.
- Response evaluable population: The subjects in the all treated population who have measurable disease at baseline and have at least one adequate post-treatment disease assessment by the investigator.
- Safety analysis population: All enrolled subjects who receive at least 1 dose of study drug (same as the all treated population).

The all treated population will be used for analyzing efficacy endpoints unless specified otherwise. The response evaluation population will be used for sensitivity analysis of efficacy endpoints. The safety population will be used for safety analysis.

9.3 Endpoint Data Analysis

9.3.1 Baseline Characteristics

Subject demographics (age, sex, race/ethnicity) and other baseline characteristics (ECOG PS, disease burden, FLIPI score) will be summarized. Summary statistics will include means, standard deviations, and medians for continuous variables and proportions for categorical variables. Compliance parameters including number of completed cycles, number of dose modifications, and reasons for discontinuation will also be similarly summarized.

9.3.2 Primary Efficacy Endpoint

The primary efficacy endpoint is PFS rate at 2 years. Response will be assessed by the investigator based on the 2014 Cheson Lugano criteria. The 2-year PFS rate will be calculated and corresponding 95% CI will be derived.

9.3.2.1 Analysis Methods

The primary analysis for all efficacy endpoints will be conducted based on the all treated population. PFS is defined as the time from the treatment start date (Cycle 1, Day 1) until the first date of objectively documented progressive disease or date of death from any cause. Patients will be censored at the last follow-up date if progression or death has not occurred during follow-up. If a patient has missing data (incomplete CT scan), all other available CT, PET/CT or MRI of the patient will be used for the analysis. Kaplan-Meier method will be used to estimate the PFS. Corresponding 95% CI will be summarized. Cox proportional hazards models will be used to assess the effects of patient prognostic factors on time-to-event endpoints. The final analysis will be performed when the last patient is followed for 3 years after last study drug dose.

9.3.3 Secondary Efficacy Endpoints

- CR rate at 120 weeks (± 4 weeks) will be determined by the PI (Cheson, Lugano classification 2014). The number and percentage of subjects with a CR at 120 weeks will be tabulated.
- ORR (CR + PR) will be assessed by the investigator based on Cheson, Lugano 2014. The number and percentage of subjects with an ORR will be tabulated. The best ORR will be recorded.
- DOR will be measured from the time by which measurement criteria for CR or PR, whichever is recorded first, is met until death or the first date by which progressive disease is documented. Subjects who are progression free and alive at the time of clinical cut-off or have unknown

status will be censored at the last tumor assessment. Subjects with no baseline disease assessment will be censored on cycle 1, day 1. Non-responders will be excluded from the analysis for DOR. Kaplan-Meier methodology will be used to estimate event-free curves, median, and 95% CI.

- EFS will be measured from the date of cycle 1, day 1 to the date of first documented progression, transformation to diffuse large B-cell lymphoma, initiation of new anti-lymphoma treatment, or death. Kaplan-Meier methodology will be used to estimate event-free curves, median, and 95% CI.
- TTNT will be measured from the date of cycle 1, day 1 to the date of first documented administration of any anti-lymphoma treatment (chemotherapy, radiotherapy, immune therapy, radioimmunotherapy, or other experimental therapy). Kaplan-Meier methodology will be used to estimate event-free curves, median, and 95% CI.
- OS will be measured from the date of cycle 1, day 1 to the date of death regardless of cause. For subjects who have not died, subjects will be censored at the time of last contact. Kaplan-Meier methodology will be used to estimate event-free curves, median, and 95% CI.

9.3.4 Safety Analysis

Analysis of safety data will be conducted on the safety population. Safety summaries will include tabulations in the form of tables and listings. The frequency (number and percentage) of treatment-emergent AEs will be reported. Additional AE summaries will include AE frequency by AE severity and by relationship to study drug.

Clinically significant abnormal laboratory values will be summarized.

9.3.5 Exploratory Analyses

The objective is to identify predictive and pharmacodynamic biomarkers after therapy with rituximab plus lenalidomide with ibrutinib in subjects with previously untreated FL and marginal zone lymphoma.

- Immunophenotyping of PBMCs to determine alteration in immune cell subsets
 - PBMC will be stained with multiple antibodies and analyzed with up to 12-parameter flow cytometry.
- Identification of signaling pathways or biomarkers that predict sensitivity or resistance by gene expression profiling (GEP)
 - GEP will be performed on tumor biopsies obtained at baseline in consenting subjects to determine predictive biomarkers. The primary focus of the analysis of GEP data will be to evaluate the 41-gene effector T cell signature previously described [36]. But other gene signatures specific to other immune cell subsets and tumor signaling pathways,

developed by our group will also be explored. Univariate Cox analysis will test whether pretreatment levels of the signature significantly correlate with PFS. If so, techniques like leave-one-out cross-validation will be applied to assess the robustness of the signature, to the extent possible in a single dataset. We will also assess its significance as compared to the predictive power of random signatures. The baseline signature will also be tested in exploratory multivariate analysis with additional variables, principally the FLIPI score, and for its ability to predict complete response. Changes in signature levels post-treatment levels will be correlated with ultimate response, and, via landmark analysis, with PFS.

- Pharmacodynamic effects of combination therapy will be assessed in peripheral blood. Blood samples will be collected at baseline, Cycle 1, Day 1, Cycle 2, Day 1, and Cycle 7, Day 1. Lenalidomide affects multiple immune cell subsets and its effects may be assessed by multiparametric flow cytometry in PBMCs as previously described [24]. Since ibrutinib has been shown to inhibit ITK in Th2 cells and skew the polarization of CD4+ T cells to Th1 phenotype, we will also assess the ratio of Th1: Th2 cells in the PBMC by intracellular cytokine assay. Furthermore, alteration of various cytokines and chemokines will be assessed in the plasma by multiplex assays. The various cellular subsets measured at baseline will be compared with on-therapy time points and correlated with best clinical response and PFS

- Determination of alteration of cytokines and chemokines

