In the phase 2 study of lenalidomide and rituximab in previously untreated FL [24], the most common hematologic adverse event was neutropenia (25% grade 3, 10% grade 4), however, febrile neutropenia was infrequent (<1%), upper respiratory infections were generally mild (21% grade 2, 2% grade 3). Common non-hematologic adverse events were fatigue (90% all grades, 5% grade ≥ 3), pain or myalgia (82% all grades, 9% grade 3), nausea or vomiting (61% all grades, 0 grade ≥ 3), rash (58% all grades, 7% grade 3), diarrhea (50% all grades, 0 grade ≥ 3), and constipation (52% all grades, 0 grade ≥ 3). Less frequent non-hematologic grade 1 or 2 adverse events included cough (44%), dizziness (43%), edema (43%), peripheral neuropathy (36%), infusion reaction (13%), and thyroid test abnormalities (23%). Second malignancies were reported in 5 patients. No deaths occurred on study as a result of toxicity.

The MTD of ibrutinib in phase 1 studies has not been reached. [28] The most common (>20%) non-hematologic adverse events associated with ibrutinib have generally been mild (Grade 1 or 2) and include diarrhea (50%), fatigue (41%), nausea (31%), peripheral edema (28%), dyspnea (27%), constipation (25%), upper respiratory infection (23%), vomiting (23%), and decreased appetite (21%). Grade ≥ 3 hematologic toxicities include neutropenia (16%), thrombocytopenia (11%), and anemia (10%). [26] Four patients in the phase 2 study that led to the FDA indication for ibrutinib in relapsed/refractory mantle cell lymphoma had subdural hematomas (Grade 1 in 1 subject, Grade 2 in 1 subject, Grade 3 in 2 subjects); all were associated with falls, head trauma, or both. [26] Though infrequent, additional non-traumatic bleeding complications associated with ibrutinib have been reported including gastrointestinal bleeding and hematuria.

Marginal zone lymphoma is a less frequent indolent NHL and is most commonly managed similar to follicular lymphoma given limited prospective data to guide routine practice. We included untreated marginal zone and small lymphocytic lymphoma in the phase 2 study of rituximab in combination with lenalidomide. [30] We enrolled 30 subjects with untreated marginal zone lymphoma subjects, 67% achieved a CR and 22% a PR with an ORR of 89%. Median PFS was 53.8 months in the subjects with marginal zone lymphoma. The median PFS in follicular lymphoma had not been reached suggesting the

Proprietary Information of MD Anderson

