combination of lenalidomide and rituximab was most promising in follicular lymphoma, but still associated with favorable outcomes in marginal zone lymphoma.

Gene expression profiling studies though limited by small number of samples have identified a set of markers with differential expression in nodal marginal zone lymphoma compared with follicular lymphoma. [31, 32] The nodal marginal zone lymphoma signature was associated with deregulated pathways including BCR signaling, interleukins (IL-2, IL-6, IL-10), integrin signaling (CD40), and cell survival pathways (MAPKs, tumor necrosis factor, transforming growth factor- β , and NF- κ B), conferring a survival advantage in nodal marginal zone lymphoma. Inactivation of the A20 gene is also a common genetic aberration in marginal zone lymphoma which may contribute to lymphomagenesis via constitutive NF- κ B signaling. [33] Alteration in lymphoma biology and signaling may explain the differences observed with therapeutic outcomes in follicular and marginal zone lymphoma. Targeting the BCR pathway may be even more attractive in marginal zone lymphoma. A phase II trial PCYC-1121 (NCT01980628) examined single agent ibrutinib in 63 patients with marginal zone lymphoma with at least one prior therapy. The results are eagerly awaited, but are anticipated to be favorable given a supplemental new drug application has been submitted to the FDA for use of ibrutinib as treatment for patients with marginal zone lymphoma. Therefore, extending the eligibility of this study to untreated marginal zone lymphoma is warranted to examine the safety and efficacy of rituximab, lenalidomide and ibrutinib in untreated marginal zone lymphoma.

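### Exploratory gene-signature test (9.3.5): a univariate Cox model over FL and MZL together leaves histology as a plausible, unadjusted confounder; stratify by histology (minor)

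*Combined protocol and SAP*

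**What the plan says.** Section 9.3.5 sets the biomarker objective "in subjects with previously untreated FL and marginal zone lymphoma". For the expression data, "The primary focus of the analysis of GEP data will be to evaluate the 41-gene effector T cell signature previously described", and the test is stated as follows: "Univariate Cox analysis will test whether pretreatment levels of the signature significantly correlate with PFS". No stratum, histology term or within-histology analysis is given. That the two histologies are pooled is inferred from this, since the section does not use the word, but it is the natural reading. Leave-one-out cross-validation follows if the test is significant, and the signature is also to be compared with random signatures. For adjustment, "The baseline signature will also be tested in exploratory multivariate analysis with additional variables, principally the FLIPI score". The five FLIPI factors in Appendix 13.7 (hemoglobin, nodal areas, age, LDH, stage) do not include histology. The same sentence extends to a complete-response analysis, again without histology.

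The assayed number is not fixed: "GEP will be performed on tumor biopsies obtained at baseline in consenting subjects".

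Section 1 says that gene-expression studies "have identified a set of markers with differential expression in nodal marginal zone lymphoma compared with follicular lymphoma". On lenalidomide plus rituximab, "Median PFS was 53.8 months in the subjects with marginal zone lymphoma", while the FL median had not been reached. The section suggests that differences in biology may account for the differences in outcome.

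**The concern.** A variable linked to both the marker and the outcome can produce an association between them when neither histology shows one on its own. If the signature runs higher or lower in MZL, and MZL progresses sooner, a univariate Cox model will tend to credit the signature with the histology difference. A positive result would then be described as a marker of sensitivity or resistance to the three-drug regimen when it might only separate FL from MZL. Leave-one-out cross-validation on the same mixed cohort would carry the same association and would not expose it. Section 9.3.5 also plans to explore other signatures, including tumor signaling pathways, and Section 1 lists B-cell receptor signaling and survival pathways as altered in nodal MZL. The same gap applies there.

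**Working it through.** **The plan's own figure.** No sample size or error rate is given for the signature analysis. The only sample-size figure, in Section 9.5, is the half-width of the 95% CI for 2-year PFS: 1.96 × √(0.77 × 0.23 / 60) = 0.1065, against 0.106 stated. It is reproduced up to rounding.

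**Inputs from the documents**
- FL 3-year PFS of 78.5% on lenalidomide plus rituximab (Section 1). Exponential hazard = −ln(0.785)/36 = 0.00672 per month.
- MZL median PFS of 53.8 months on the same regimen (Section 1). Hazard = ln(2)/53.8 = 0.01288 per month.
- Implied hazard ratio, MZL to FL: 0.01288/0.00672 = 1.92. Implied 24-month PFS: exp(−24 × 0.01288) = 73% in MZL and exp(−24 × 0.00672) = 85% in FL.
- 60 patients at 4 per month, so 15 months of accrual (Section 9.5).
- Final analysis 3 years after the last patient's last dose (Section 9.3.2.1). Twelve 28-day cycles are about 11 months, so follow-up runs from 11 + 36 = 47 to 47 + 15 = 62 months.

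**Inputs assumed, because the documents give none:** MZL share 10–40%; difference in mean signature between histologies 0 to 2 SD; 30 or 60 patients assayed.

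**Method.** Simulate trials with no signature effect within either histology, and count how often a two-sided 5% Cox score test rejects, pooled and then stratified by histology. There are 3,000 trials per setting, so the Monte Carlo standard error is √(0.05 × 0.95/3000) = 0.4 percentage points at 5%.

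| Assayed | MZL share | Test | 0 SD | 0.5 SD | 1 SD | 1.5 SD | 2 SD |
|---|---|---|---|---|---|---|---|
| 60 | 10% | pooled | 5.4% | 5.9% | 6.7% | 8.3% | 9.7% |
| 60 | 25% | pooled | 5.1% | 5.8% | 9.6% | 13.4% | 17.6% |
| 60 | 25% | stratified | 5.0% | 5.2% | 6.0% | 5.3% | 4.8% |
| 60 | 40% | pooled | 5.0% | 7.1% | 9.9% | 15.9% | 21.9% |
| 30 | 25% | pooled | 5.0% | 6.6% | 7.4% | 8.7% | 11.7% |

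Repeat runs put the 60-patient, 25% MZL setting at 9–10% (1 SD) and 17–18% (2 SD), and the 30-patient setting at up to about 8% and 13%. With a minimum follow-up of 36 months, the 60-patient, 25% MZL figures are 8.8% and 15.2%. Stratification held the rate at roughly 4–6% throughout.

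**Sensitivity to the outcome gap.** At a hazard ratio of 1.3 the pooled rate is about 5–7.5% over 30 or 60 patients, 10–40% MZL and shifts up to 2 SD.

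**The random-signature comparison.** Suppose a finding must both reach p < 0.05 and fall in the top 5% against 200 random signatures (60 assayed, hazard ratio 1.92). If the random signatures shift by histology as much as the target does, the false-positive rate falls from 9.5% to 5.3% (1 SD, 25% MZL), from 16.8% to 4.7% (2 SD, 25%), from 12.0% to 5.6% (1 SD, 40%) and from 21.6% to 4.3% (2 SD, 40%). If they shift by only 0.5 SD, it falls from 9.2% to 7.2% with the target at 1 SD, and from 17.0% to 12.9% with the target at 2 SD.

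**The case against.** The strongest reply has four parts.

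First, a reader might infer that the protocol itself establishes histology as a confounder of this signature. It does not. The expression statement in Section 1 concerns nodal MZL, rests on studies that the protocol itself describes as small, and does not mention effector T cells. Inclusion criterion 1 admits any MZL. With no shift in this signature there is no inflation. This stands: the confounding is plausible, not shown.

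Second, the PFS gap comes from lenalidomide plus rituximab without ibrutinib, combines figures cited to two different reports, and needs an exponential assumption. Section 1 suggests that targeting the B-cell receptor pathway may be especially attractive in MZL, so the gap may narrow. This also stands, and the hazard ratio of 1.3 shows how much it matters.

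Third, a reader might infer that the random-signature comparison is no help because random signatures would also separate FL from MZL. That reasoning runs the wrong way. If they do, they carry the same confounding and the target no longer stands out. Protection is full when they track histology as strongly as the target does, and partial when they track it less.

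Fourth, the list of additional variables in 9.3.5 is open, and Section 9.3.2.1 provides Cox models for prognostic factors, so histology could be added. Neither place names it, however, and the test that leads to cross-validation would remain univariate.

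**Conclusion.** The point holds as a minor improvement to an exploratory analysis. The stated test cannot account for histology, and Section 1 gives reason to think that both expression and outcome may differ by histology. At a hazard ratio of 1.92 with 25% MZL and 60 assayed, the false-positive rate is about twice nominal at a 1 SD shift (9–10%) and between three and four times nominal at 2 SD (17–18%). With 30 assayed it is about 8% and 13%. These sizes rest on an assumed MZL share, shift and number assayed, and on a hazard ratio borrowed from a regimen without ibrutinib. Tissue depends on consent, so the 60-patient figures are an upper case. A reader might go further and see a threat to the trial's main conclusion. The documents do not support that, because the signature is an exploratory endpoint and governs no sample size, stopping rule or primary result.

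**What to change.** In Section 9.3.5:
- Make the signature–PFS test a Cox model stratified by histology (FL versus MZL).
- Use the same stratification in the random-signature comparison and the cross-validation.
- Add histology to the complete-response model, with FLIPI as a further covariate.
- Report the FL-only estimate beside the stratified one.

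The cost is SAP wording and one strata term. Histology is known for every patient from inclusion criterion 1, and fixing the choice in advance avoids a post hoc one. The downside is a slight loss of information when the MZL stratum has few events. With 60 assayed and 25% MZL (15 patients), mean follow-up of about 54.5 months gives roughly 15 × (1 − exp(−0.01288 × 54.5)) = 7.6 MZL events out of about 21 in all. With 30 assayed it would be about half that.
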